This study will provide rigorous epidemiologic evidence regarding the influence of fetal exposure to HIV and ART on developmental and mental health outcomes from infancy to adolescence, including obtaining a national population-based estimate of HEU burden of developmental and mental health outcomes and strategies for programmatic surveillance and referral.

11. Specific aims and hypotheses

Aim 1: Within a longitudinal cohort of 1000 HEU and 1000 HUU infants enrolled at 6 weeks of age from 5 MCH clinics and followed 6-monthly:

HOPE study protocol

Version 1.3

July 21, 2020

Aim 1a. To compare HEU and HUU infants and children for growth, hearing, and neurodevelopmental outcomes; and determine influence of ART timing/regimen on HEU outcomes. To determine whether fetal HIV/ART exposure impacts 4-year neurodevelopmental outcomes; and assess impact of peripartum ART regimen and timing.

Aim 1b: To compare telomere length in HEU and HUU and determine associations with neurodevelopmental outcomes.

Aim 2a: To determine the impact of HEU and HUU status, as well as maternal peripartum ART, on neurodevelopment and mental health (ASD, ADHD, depression, and anxiety). We will pilot a mobile screening strategy to detect adverse neurodevelopmental and mental health outcomes in HEU for use in large-scale screening in Aim 2b. Mothers attending HIV care will be invited to bring their HEU (aged 3-18) (200 HEU, 50 per age-stratum: 3-6, 7-10, 11-14, 15-18) for screening; age- matched HUU will be recruited from the community.

Aim 2b. To estimate population-burden and cofactors of adverse neurodevelopmental and mental health outcomes in HEU using mobile teams to screen HEU in ~100 large HIV Care Clinics throughout Kenya (4000 HEU; age-stratified, 3-6, 7-10, 11-14, 15-18) and 400 age-stratum matched community HUU.

Aim 3. To estimate the cost of this screening strategy and convene stakeholders to review data regarding programmatic integration of HEU screening.

12. Study design and methodology

a. Study area description

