6. Interested mothers give informed consent to participate
7. Study staff conduct HIV testing for mothers if HIV status not available in mother-baby maternal and child health booklet
8. Study staff collect contact and locator information
9. Study staff collect enrollment data - demographics, HIV status, pregnancy history, ART use and history
10. Study staff conduct anthropometric measures, neurodevelopmental and mental assessments, hearing tests on infant and collect DBS
11. Study staff reimburse client and give appointment for the next visit

v. Laboratory methods

Blood samples: Dried blood spots (DBS) for assessment of telomere length will be collected at enrollment and 12 monthly either using finger prick or venous blood draw (0.5ml).

vi. Data collection instruments

Socio-demographic, pregnancy and post-partum data: Socio-demographic information, family characteristics, medical history (including HIV status), mental health history and substance use history will be collected from caregivers. We will assess for caregiver depression at every visit using PHQ-9.

Growth assessments: Standard anthropometric measures including weight, height/length, head circumference and mid-upper arm circumference will be assessed by trained study staff. These measures will be converted to standard Z-scores using the WHO growth standards.

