Telomere length analyses Telomere length (TL) may reflect prior fetal exposure to inflammation. In one study PHIV had significantly shorter TL than HEU and HUU children; untreated PHIV had shorter TL than those on ART¹⁶⁰. Among HEU infants, TL was significantly shorter among those whose mothers were untreated in pregnancy than those whose mothers received zidovudine monotherapy and maternal viremia was inversely associated with infant TL¹⁶¹. TL was significantly shorter in South African PHIV (ART-treated) and HEU children than in HUU (mean age 6.4 years)¹⁶². However, not all studies have demonstrated associations between HEU and TL. One study found no difference in TL between PHIV, HEU, and HUU children, although TL shortening was associated with viremia in PHIV¹⁶³. Similarly, there were no significant differences in TL between HEU and HUU children in a recent Canadian study¹⁶⁴. There is also evidence that maternal IPV or adverse childhood experiences (ACEs) influence infant TL^{165,166}. This evidence is limited by differences in exposure and outcome measurements¹⁶⁷⁻¹⁶⁹. TL shortening has been associated with emotional processing on fMRI¹⁷⁰ and with ADHD and depression¹⁷¹⁻¹⁷⁴. **A molecular signal such as TL shortening could reflect ‘archived’ history of fetal HIV exposure to further support associations with HEU.** *Telomere length assessment:* DNA will be extracted from DBS in the University of Nairobi Pediatric Research laboratory prior to shipping to the [name] lab for TL assessment; the [name] lab has extensive experience conducting TL assays. Methods for TL assessment using DBS have been recently developed by Rej et al (*in press*) in the UW [name] lab, who has shared these methods with the [name] lab. Analysis: We will compare TL from 500 HEU and 500 HUU in Aim 1 cohort at 6 weeks, 1, and 4 years of age and compare TL between infants with neurodevelopmental compromise (or with ASD) to those without; overall, and stratified by HEU/HUU status. DBS will be collected in cross-sectional survey of older HEU from 20 sites for future studies, conditional on evidence from Aim 1 results. We will use linear regression to compare TL in HEU to HUU and conditional linear regression for comparisons of neurodevelopmental outcomes; with multivariate adjustment for cofactors as previously described.

d. Aim 2

i. Study design

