Cognitive outcomes. Cognitive assessments will be done using NIH Toolbox. The battery will include the tests Dimensional Change Card Sort Test, Flanker Inhibitory Control and Attention Test, List Sorting Working Memory Test, Pattern Comparison Processing Speed Test, and Picture Sequence Memory Test, which evaluate working memory, attention, processing speed, and other aspects of executive functioning. The NIH Toolbox has been validated for US children and was recently adapted through a rigorous process involving translation and backtranslation for Kenya, including translation to Dholuo and Kiswahili.

The table below summarizes the tools, age-group they are used in, screening time and domains or disorders they test.

Tool	Age-group	Time (minutes)	Types	Domains/Disorder
MDAT	0.6-5	30	Screening	Gross motor, fine motor, language, social
HearScreen TM	3+	5	Screening	Hearing
NIH Toolbox	6-17	25-30	Screening	working memory, attention, processing speed, executive functioning
Strengths and difficulties questionnaire (SDQ)	3-16 & caregivers	10	Screening	Emotional symptoms, conduct problems, hyperactivity/inattention, peer relationship problems
SNAP-IV	6-12	5-10	Screening	ADHD
PHQ-9	>16 & caregivers	3	Screening	Depression
MINI-KID	6-17	10	Diagnostic	Common psychiatric conditions
MINI	18	10	Diagnostic	Common psychiatric conditions
School performance	>10	1	NA	National exam results Parental report

vii. Sample size determination & data analysis

Effect size calculations: For comparisons of z-scores in MDAT or NIH-toolkit scores, we will be able to detect differences of 0.13-0.18 assuming a standard deviation of 1.0 or 1.4, 80% power and alpha of 0.05 in Aim 1 cohort (Table 10). In the cross-sectional cohort, 2- to 3-fold differences will be detectable, in diagnoses such as depression and ADHD. To detect smaller differences, more HUU could be enrolled in some age-strata based on pilot feasibility.

R61/R33 Aim 1 cohort	Effect detectable (no attrition)		Effect detectable (20% attrition)	Assumptions
Difference in z-score for MDAT	0.13 (SD=1.0)	1000 HEU:1000 HUU	0.14 (SD=1.0)	Standard deviation = 1.0-1.4 ¹⁰⁵
	0.18 (SD=1.4)		0.20 (SD=1.4)	
Difference in ASD prevalence	2.2%	1000 HEU:1000 HUU	2.5%	HUU ASD 2%
	3.3%	500 DTG: 500 EFZ	3.8%	
Difference in SDQ+ prev.	5.2%	1000 HEU:1000 HUU	5.9%	HUU SDQ+ 20%
	7.5%	500 DTG: 500 EFZ	8.5%	
Difference in hearing loss	1.7%	1000 HEU:1000 HUU	2.0%	HUU 1%
	2.7%	500 DTG: 500 EFZ	3.1%	
Difference in TL	0.18	500 HEU: 500 HUU		SD=1.0

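### Aim 1b relates telomere length to neurodevelopment only through a binary split and an unexplained conditional regression; regression on the continuous MDAT z-scores in the same children would detect a weaker association at no cost.

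*Protocol*

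**What the plan says.** Protocol section 11 gives Aim 1b two parts: "To compare telomere length in HEU and HUU and determine associations with neurodevelopmental outcomes".

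Section 12.c.vii, under Telomere length analyses, sets out both. The exposure part reads "We will compare TL from 500 HEU and 500 HUU in Aim 1 cohort at 6 weeks, 1, and 4 years of age". The same sentence goes on to the outcome part: "compare TL between infants with neurodevelopmental compromise (or with ASD) to those without; overall, and stratified by HEU/HUU status". HEU versus HUU is to be compared by linear regression, and the outcome part by "conditional linear regression for comparisons of neurodevelopmental outcomes", with multivariate adjustment for the cofactors listed earlier.

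Four related statements bear on this:

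- Under Neurodevelopmental outcomes in section 12.c.vii, the four MDAT domains are analysed as z-scores by linear regression.
- Section 12.c.v says that dried blood spots "will be collected at enrollment and 12 monthly", with no restriction to a subset. The Aim 1 data collection table agrees.
- The effect-size table in section 12.d.vii has one telomere row, labelled "Difference in TL", for "500 HEU: 500 HUU": 0.18 at SD 1.0, with the attrition cell empty. The table assumes 2% ASD in HUU.
- Section 9 mentions nested case-control studies in general terms, without linking them to telomere length.

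**The concern.** The outcome part of Aim 1b is stated only as a comparison of two groups. One component, neurodevelopmental compromise, is a cut through a score that is measured on a continuous scale at every visit. Cutting it loses information, and the protocol gives no cut-off from which to judge how much. The other component, ASD, is a rare screening result.

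The model does not match the design as described. A conditional regression needs matched or otherwise defined sets to condition on, and none is given for TL.

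At stake is whether a null result could be interpreted. The protocol's one TL power figure concerns a different contrast, so nothing in it tells the reader how large a TL-outcome association the study could see.

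**Working it through.** **Inputs from the protocol.** "80% power and alpha of 0.05 in Aim 1 cohort"; TL SD 1.0; 500 HEU and 500 HUU assayed; ASD 2% in HUU; a detectable ASD excess of 2.2 points at 1000:1000, so 4.2% in HEU; 20% attrition as the alternative scenario.

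**Assumptions.** Two-sided test, normal approximation, no site clustering, subset drawn without regard to outcome. The MDAT cut-offs are illustrative because the protocol gives none.

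**1. Reproduce the plan's figure.** Detectable difference d = (1.960 + 0.842) x SD x sqrt(1/n1 + 1/n2). At 500 v 500: 2.802 x sqrt(2/500) = 0.177, which rounds to the stated 0.18.

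**2. ASD contrast in the assayed 1000.**

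| Scenario | Cases v rest | Detectable d (SD) |
|---|---|---|
| 2% in both groups | 20 v 980 | 0.63 |
| 2% HUU, 4.2% HEU | 31 v 969 | 0.51 |
| Within HUU, 2% | 10 v 490 | 0.89 |
| Within HEU, 4.2% | 21 v 479 | 0.62 |
| 20% attrition, 2% in both | 16 v 784 | 0.71 |
| 20% attrition, 4.2% HEU | about 25 v 775 | 0.57 |

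**3. Compromise contrast, n = 1000, under assumed cuts.**

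| Assumed definition | Cases | Detectable d (SD) |
|---|---|---|
| One domain, z < -2 | 23 | 0.59 |
| One domain, z < -1.5 | 67 | 0.35 |
| One domain, z < -1 | 159 | 0.24 |
| One domain, z < -2, MDAT SD 1.4 | 77 | 0.33 |
| Any of four independent domains, z < -2 | about 88 | 0.31 |

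**4. Split against continuous score, same 1000 children.** For a standard normal score cut at c with tail proportion p, the groups differ in mean score by phi(c)/[p(1-p)]. Dividing d by this gives the correlation that the split needs.

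- c = -2, p = 0.023: mean difference 2.43; 0.594/2.43 = 0.24.
- c = -1, p = 0.159: mean difference 1.81; 0.242/1.81 = 0.13.
- Continuous score: 2.802/sqrt(1000) = 0.089, about 0.09 (0.10 with 800 children; about 0.125 within one group of 500).

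The share of information kept by the split is phi(c)^2/[p(1-p)]: 0.131 at c = -2 and 0.439 at c = -1.

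**5. Adding ASD screen-positives from outside the subset.** The whole cohort would hold about 40 (2% in both groups) to 62 (4.2% in HEU). Then 40 v 980 detects 0.45 SD and 62 v 969 detects 0.37 SD. Power for a 0.5 SD difference rises from 60% to 87% in the first case and from 78% to 97% in the second. Within HUU, 20 v 490 still detects only 0.64 SD.

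**6. The model.** If the 500 + 500 are chosen without regard to outcome, a conditional model has no sets to condition on. If they are case-selected or matched, HEU versus HUU is no longer a plain 500 v 500 comparison, and 0.18 does not directly apply. The text needs revision either way.

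**The case against.** A reader might infer that Aim 1b leaves about 20 cases, throws away the MDAT z-scores, never uses the stored spots of the other ASD cases, and is therefore almost certain to be uninformative. The protocol does not support that.

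- **Case count.** Twenty is the ASD count alone, with the HUU figure of 2% applied to both groups. The group defined by compromise or ASD cannot be counted without a cut-off. On one domain with SD 1, compromise alone gives about 23 to 159 under the cuts tried.
- **MDAT z-scores.** They remain the primary Aim 1 outcome. The aim is worded broadly enough to allow a continuous TL analysis, and the regression sentence does not exclude one. None is stated, however.
- **Stored spots.** The method of choosing the 500 + 500 is not given. The general mention of nested case-control studies, together with the word conditional, is compatible with case-based sampling. That spots go unused is an inference from outcome-blind selection.
- **Uninformative.** This is fair for the ASD and within-stratum contrasts. It is too strong for MDAT at a mild cut-off.

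It can also be said that the cut-off, the subset selection and the final model are commonly left to an analysis plan, that TL is not in Table 6, and that the effect-size table claims nothing false about this contrast. All of that stands. What remains is that the protocol does state a contrast and a model for this question. The contrast is less sensitive than one the same data allow, and the model does not fit any design described.

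**Conclusion.** The point holds as a free improvement to a stated analysis. The only stated TL-neurodevelopment comparison is binary, its main component is undefined, and its model presupposes matching that is not described. Using the continuous MDAT z-score would lower the detectable correlation to about 0.09, from about 0.24 (cut at z < -2) or 0.13 (z < -1). These figures assume a linear, normal relation. If TL differed only among the most impaired children, the binary contrast would be the relevant one, which is a reason to keep it as secondary.

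The ASD contrast is weak under either prevalence assumption: about 0.5 to 0.6 SD overall without attrition, and about 0.9 SD within HUU. ASD here means high risk on the M-CHAT-R/F screen, not a diagnosis. This part, and the gain from assaying further cases, depends on outcome-blind selection of the subset and is the secondary part of the point.

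**What to change.** 1. **Main change.** Make the main TL-neurodevelopment analysis an ordinary linear regression relating TL to the continuous MDAT domain z-scores in all assayed children, with an HEU/HUU interaction and the stated cofactors. Delete the word conditional unless a matched design is specified. Keep the compromise/ASD contrast as secondary, with a stated cut-off. This is a wording change and needs no new data.

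2. **State how the 500 + 500 are chosen.** This too is a wording change, and it settles whether item 3 applies.

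3. **Optional, if selection is without regard to outcome.** Draw the 500 + 500 as a random subcohort within HEU and HUU, add the stored spots of ASD screen-positives outside it, and analyse ASD as a case-cohort comparison. Keep the HEU versus HUU contrast in the random subcohort. The cost is about 20 to 31 more children at three time points, so 60 to 93 assays on top of 3000 (2% to 3%). If the assay budget is fixed, a subcohort of n per group with 2n + (1000 - n) x 0.04 = 1000 gives n of about 490 at 2% in both groups; replacing 0.04 by 0.062 (4.2% in HEU) gives about 484. The HEU versus HUU detectable difference then moves from 0.177 to 0.179 or 0.180 SD. Within-stratum ASD contrasts would stay weak and should be described as exploratory.

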Cross-sectional surveys. These will be done in 2 phases 1) Pilot phase and 2) Population phase. The pilot phase will be conducted in one facility (Rachounyo sub-County hospital) after which we will begin population based assessments in 100 large HIV clinics. Procedures for enrollment and assessment are similar for 2 phases.

HOPE study protocol

Version 1.3

July 21, 2020

ii. Study populations

HEU and HUU caregiver-child pairs

iii. Recruitment procedures

MLHIV attending HIV Care clinics will be asked about potentially eligible HEU children aged 3-18 by study nurse. MLHIV who are interested in participating will be invited to return with their child/adolescent for participation in the study. Study nurses will also liaise with clinic community health workers (CHWs) to recruit eligible HUU in the relevant age strata (3-6, 7-10, 11-14, 15-18 years) in the community. CHWs will invite mothers of eligible HUU children to participate in the study for evaluation and mother-child/adolescent pairs will be enrolled at a neutral site (typically MCH or family planning [FP] clinic) or at home. Study nurses will be accompanied by the community health worker for home enrollments. A standard recruitment form will be used.

The target enrollment is 400 children and adolescents (200 HEU and 200 HUU) in the pilot phase and 4400 (4000 HEU and 400HUU) age 3-18 years (stratified to the following groups: 3-6, 7-10, 11-14, 15-18 and by HIV status (HEU or HUU)) in the population phase. The pilot phase will be conducted in one facility in rural Kenya (Rachuonyo Hospital HIV clinic), and the population phase in 100 large HIV care clinics with at least 1000 adult women in HIV care.

For HEU, caregivers attending HIV clinics who have children in the proposed age-groups will be recruited by the clinic staff. Caregivers who are interested will meet with the study nurse and be provided with details on the study and study procedures and invited to bring children for enrollment. All study procedures will be completed at enrollment with no follow-up procedures.

HUU will be recruited from the neighboring community around the HIV Care Clinic from where the HEU are recruited. Nurses and Community health workers (CHW) will visit households to recruit interested caregivers of children age 3-18 and enroll those who meet eligibility criteria and are willing to confirm HIV status (using HIV self-test kits) and enroll their children in the study.

Eligibility criteria

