Child or adolescent age 3-18 years

Child/adolescent is healthy and HIV negative

Mother HIV status known

Mother HIV diagnosis and ART timing known (for HEU)

Caregiver \geq 18 years willing to take children to clinic for evaluation

iv. Enrollment and study procedures

Enrollment will be conducted at a neutral location (typically public MCH clinic) or at home. No additional visits will be conducted after enrollment.

Determination of HIV status for HEU and HUU: A combination of medical records and HIV testing will be used to determine HIV status of mothers and children. Maternal HIV-positive status during the pregnancy with each child will be determined first using the mother-baby maternal and child health booklet; in the event that this

HOPE study protocol

Version 1.3

July 21, 2020

booklet is not available, records from the HIV care clinic documenting the date when the mother was diagnosed with HIV or started ART will be used (only for HIV positive mothers). In the event of no records are available, maternal report of being diagnosed with HIV either during or prior to the pregnancy with each child will be used (only for HIV positive mothers). For mothers who report not being HIV positive at the time of pregnancy and for whom mother-baby maternal and child health booklets are not available, we will offer maternal HIV testing; mothers who do not consent to HIV testing will not be enrolled.

For HEU dyads, children's HIV negative status will be determined using the same set of procedures (first reviewing mother-baby maternal and child health booklet, then infant HIV testing history records); if the child has not been tested for HIV after the cessation of breastfeeding, HIV testing will be offered for the child. Children ages 7-14 years will be asked to provide assent without mention of HIV; children ages 15-18 will be asked to provide assent (or consent for 18 year olds) with explicit mention of HIV testing and will be told that they can choose whether they wish to share their results with their caregivers. If children decline HIV testing, they will not be enrolled in the study.

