For HUU dyads, children will be assumed to be HIV negative if their mother is negative and if they are <15 years of age. Children ages 15-18 will be asked to provide assent (or consent for 18 year olds) with explicit mention of HIV testing and will be told that they can choose whether they wish to share their results with their caregivers. If children decline HIV testing, they will not be enrolled in the study.

At enrollment, growth, neurodevelopmental and mental health outcomes will be collected by interviews with caregivers/adolescents/children. For HIV positive mothers, additional details on HIV treatment history, ART regimen, perinatal illnesses and general health will be obtained from medical records.

Caregivers and adolescents age 18 will give informed consent to participate in the study. Children and adolescents age 7-17 will give assent to participate.

At enrollment, study staff will perform anthropometric measurements (height/weight/head circumference, MUAC), neuro-developmental, mental health and hearing screening and assessments and collect data on past and current child comorbidities and nutrition. Children and adolescents who fail screening tests will be referred for further evaluation as needed.

Summary of procedures for recruitment and enrollment

1. MCH nurse or CHW reads recruitment script to potential participant
2. MCH nurse or CHW refers interested participant
3. MCH nurse or CHW documents reason for declining to participate
4. Study nurse assesses eligibility
5. Study nurse gives more information on the study
6. Interested mothers give informed consent to participate
7. Children age 7 and above give assent to participate
8. Determine maternal and/or child HIV status using medical records
9. Conduct maternal and/or child HIV testing, if not determined using medical records
10. Study staff collect enrollment data - demographics, pregnancy history, ART use and history
11. Study staff conduct anthropometric measures, neurodevelopmental and mental assessments, hearing tests and collect DBS
12. Study staff reimburse client

v. Laboratory methods

HOPE study protocol

Version 1.3

July 21, 2020

Blood samples: Dried blood spots (DBS) for assessment of telomere length will be collected either using finger prick or venous blood draw (0.5ml) at enrollment in 20 selected sites.

HIV testing: HIV testing will be conducted using saliva-based HIV tests, administered by a health care worker.

vi. Data collection instruments

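### Aim 2 gives no single rule for HUU status: under the booklet route, HUU children under 15 are taken as HIV negative from an undated maternal result, so some breastfeeding-exposed, late-pregnancy-exposed or infected children could enter the small comparison group unseen

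*Protocol*

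**What the plan says.** All references are to protocol section 12.d (Aim 2).

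- **Recruitment procedures (iii).** HUU children come from households around the HIV clinic. Their caregivers must meet the eligibility criteria and be "willing to confirm HIV status (using HIV self-test kits) and enroll their children in the study". Holding a booklet is not mentioned as an exemption.
- **Eligibility criteria (iii).** The child must be HIV negative and the mother's HIV status known. No date is attached to that status.
- **Determination of HIV status (iv).** "Maternal HIV-positive status during the pregnancy with each child will be determined first using the mother-baby maternal and child health booklet". A mother who reports having been negative in the pregnancy is tested only in the group "for whom mother-baby maternal and child health booklets are not available, we will offer maternal HIV testing".
- **Summary of procedures (iv), steps 8-9.** Records come first, then: "Conduct maternal and/or child HIV testing, if not determined using medical records".
- **HUU child status (iv).** "children will be assumed to be HIV negative if their mother is negative and if they are <15 years of age". For ages 15-18 testing is a condition of entry: "If children decline HIV testing, they will not be enrolled in the study".
- **HEU child status (iv).** Booklet and infant testing records are reviewed, and "if the child has not been tested for HIV after the cessation of breastfeeding, HIV testing will be offered for the child".
- **Laboratory methods (v).** "HIV testing will be conducted using saliva-based HIV tests, administered by a health care worker".

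**The concern.** A team following the recruitment text would test every HUU caregiver. A team following the status-determination text would not test a mother whose booklet shows a negative result. With about 100 clinics, both practices can be expected.

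The choice matters because the under-15 assumption is only as good as the maternal result behind it. A negative result today rules out maternal infection during that pregnancy and during breastfeeding. A negative entry from the pregnancy does not rule out infection later in the pregnancy or while the child was breastfed. The plan guards against this for HEU children with the post-breastfeeding test, but writes no matching check for HUU children under 15.

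At stake is the small arm of the Aim 2 HEU-HUU comparisons: 100 HUU against 1000 HEU per age stratum. If HEU children do worse, exposed or infected children within HUU pull the contrast toward no difference. The protocol's background section says it hopes for reassuring findings, so this is the awkward direction.

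**Working it through.** No sample size or power figure in the plan rests on this rule. The check is therefore a comparison of texts, followed by a count and an illustration.

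**1. The two routes, case by case (HUU child under 15)**

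- *Booklet negative, mother negative now.* Both routes admit the child, correctly.
- *Booklet negative, mother infected after weaning.* A test now would be positive, and the recruitment text does not say what follows. The booklet route admits the child. That is right for fetal exposure, and there was no breastfeeding exposure.
- *Booklet negative, mother infected later in pregnancy or during breastfeeding.* A test now would reveal it. The booklet route admits the child untested. This is the case that matters.
- *No booklet, mother reports negative in the pregnancy.* Both routes test her. Neither says how the child is classified if she is positive now.

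**2. How many children the untested route can cover**

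The strata are 3-6, 7-10, 11-14 and 15-18, and the last is tested.

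- Survey: 3 x 100 = 300 of 400 HUU.
- Pilot: 3 x 50 = 150 of 200, assuming HUU are split equally like the HEU.
- Together: up to 450 of 600.

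These are ceilings on children whose status could rest on the booklet. They are not counts of misclassified children. The actual number depends on booklet availability and on maternal infection in the relevant window, and the protocol gives neither.

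**3. Illustration of size (assumed inputs)**

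Yardstick: section 12.d.vii states a detectable difference of 0.29 for a continuous score with 1000 HEU, 100 HUU and SD 1. Check: (1.960 + 0.842) x sqrt(1/100 + 1/1000) = 2.802 x 0.1049 = 0.294, in agreement. Power at exactly 0.29 is 79.0%.

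Assume maternal incidence of 0.3-1% per year, 3-6 months of pregnancy left after the booklet test, and two years of breastfeeding.

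- Late pregnancy: 0.3% x 0.25 = 0.08% to 1% x 0.5 = 0.5% of mothers.
- Breastfeeding: 0.3% x 2 = 0.6% to 1% x 2 = 2% of mothers.
- Sum: about 0.7-2.5%, or 2 to 7.5 of 300 children if all entered by booklet.

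If a fraction c of HUU has the HEU mean, the observed difference is (1 - c) x the true difference. At c = 0.025, 0.29 becomes 0.29 x 0.975 = 0.283. Power is then Phi(0.283/0.1049 - 1.960), about 77%. For late-pregnancy exposure alone, c is at most 0.005.

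This treats every breastfed child of a newly infected mother as HEU-like, which is generous. An infected child could differ by more than an HEU child, but would be only a fraction of these.

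**The case against.** **The contradiction may be only apparent.** The recruitment text asks for willingness to confirm status, while the status-determination text is the operating rule. Read together, all must be willing and those without records are tested. This reading is fair and softens the conflict. It does not close the gap, because it is the reading under which booklet holders go untested.

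**The exposure is fetal, so status in pregnancy is the right time point.** This largely stands. A reader might add up ten years of maternal incidence and conclude that 3-10% of HUU are misclassified and the contrast shrinks by as much. The documents do not support that. A mother infected after weaning leaves a correctly classified HUU child, ten years cannot apply to the 3-6 stratum, and no incidence is given.

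**HUU children are not all untested.** Correct: ages 15-18 must accept a test.

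**The under-15 rule requires that the mother is negative, in the present tense.** On that wording a mother known to be positive now does not qualify, which narrows the gap to infections not known to the study. Nothing says how negative now is established when a booklet is accepted.

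**Caregiver versus mother.** A reader might infer that another caregiver's test could stand in for the mother's. The same recruitment text speaks of inviting mothers and enrolling mother-child pairs, and section iv specifies maternal testing. This is loose wording, not a second rule.

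**Self-test versus health worker.** The kit name may describe the product and the laboratory text who gives it. One sentence settles it.

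**Conclusion.** The point holds as an inconsistency with a limited consequence. The Aim 2 text does not state one HUU rule. The version in the status-determination section can admit late-pregnancy-exposed, breastfeeding-exposed or infected children under 15 to HUU without detection; an infected child would also breach the plan's own requirement of an HIV-negative child. Up to 300 of 400 survey HUU could have their status set this way.

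The likely bias is toward no difference, if HEU children do worse, and is probably small. Under the assumed inputs above it shrinks the contrast by at most about 2.5%, and by no more than 0.5% for missed fetal exposure. These figures rest on an assumed incidence and assumed windows, so they show scale only. The inconsistency is certain; the size of the bias cannot be computed from the protocol. This is a cheap improvement. It does not show that the Aim 2 comparison is invalid.

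**What to change.** Reconcile the recruitment, status-determination and laboratory texts of section 12.d into one rule.

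1. The biological mother of every HUU child takes the already foreseen HIV test at enrolment, whatever the booklet shows.
2. A negative result confirms HUU status and supports the under-15 assumption.
3. If she is positive now, the child counts as HUU only when records show she was negative through that pregnancy and breastfeeding. If breastfeeding exposure cannot be excluded, the child is tested or left out of the HUU contrast. Excluding every mother who is positive now is not needed, since it would discard validly unexposed children.
4. Write biological mother in place of caregiver in the recruitment text.
5. State one test procedure, reconciling self-test kits with administration by a health care worker.

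Cost: protocol wording and testing of up to 200 pilot and 400 survey HUU mothers, for whom the recruitment text already foresees kits. Some booklet holders will decline the test and need replacing.
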